A Phase II Clinical Study of First-Line Immunotherapy Combined with Chemotherapy for Advanced Small Cell Lung Cancer

Study Protocol

Protocol Number: Version Number: 1.1

Date of Document: January 7, 2021

Clinical Trial Sponsoring Organization: Shanghai Pulmonary Hospital Clinical Trial Data Statistics Organization:

Clinical Trial Applicant Organization: Shanghai Pulmonary Hospital

Protocol Summary

Study Title	A Phase II Clinical Study of First-Line Immunotherapy Combined with Chemotherapy for Advanced Small Cell Lung Cancer
Study Number	
Version Number	1.1
Responsible Organization	Shanghai Pulmonary Hospital
Principal Investigator	[name]
Study Subjects	Patients with Advanced (Extensive-Stage) Small Cell Lung Cancer
Purpose of the Study	 Main Objective: To evaluate the 1-year Progression-Free Survival (PFS) rate of subjects receiving first-line treatment with PD-1 inhibitor combined with chemotherapy. Secondary Objectives: To assess Progression-Free Survival (PFS), Overall Survival (OS), and Objective Response Rate (ORR) of subjects according to RECIST 1.1; To evaluate the quality of life of subjects based on the EORTC QLQ-C30 scoring; To assess the incidence of adverse events (AEs) in subjects. Exploratory Objectives: To identify potential predictive biomarkers for the efficacy of immunotherapy in the treatment of advanced (extensive-stage) small cell lung cancer.
Study Design	This study is a single-center, prospective, single-arm, open-label Phase II clinical study to observe the efficacy and safety of Sintilimab combined with chemotherapy in previously untreated extensive-stage small cell lung cancer (SCLC) subjects. The trial plans to enroll 45 patients.

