The primary endpoint of this study is the 1-year PFS rate, defined as the proportion of patients without disease progression at one year.

Sample Size

Based on previous research data, the 1-year PFS rate for patients with extensive-stage SCLC receiving first-line chemotherapy does not

Estimation

exceed 5.4%. It is estimated that the use of first-line Sintilimab combined with chemotherapy can increase the 1-year PFS rate of patients to 15%. Through sample size calculation, with α =0.05 (one-sided test), Power=80%, and assuming a dropout rate of 10%, using the One-Sample Logrank Test, a total of 45 patients are required to be enrolled.

- (1) Age: ≥18 years and ≤75 years old;
- (2) A confirmed diagnosis of extensive-stage small cell lung cancer (SCLC) by pathological examination (including histology or cytology);
- (3) Previously untreated patients who have not received any systemic antitumor therapy;
- (4) Asymptomatic patients with brain metastases, or those with brain metastases that have been treated and maintained a clinically stable condition for at least one month, and have not used corticosteroids and anticonvulsant medications for at least one month prior to entering the study;
- (5) Measurable lesions (as defined by RECIST 1.1, the long diameter of the tumor lesion on CT scan is ≥10mm, the short diameter of the lymph node lesion on CT scan is ≥15mm, the scan slice thickness is no more than 5mm, and the measurable lesions have not received local treatments such as radiotherapy or cryotherapy);

Inclusion Criteria

- (6) ECOG PS: 0-2;
- (7) Estimated life expectancy ≥3 months;
- (8) Adequate hematological function, defined as an absolute neutrophil count of ≥1.5×10^9/L, a platelet count of ≥80×10^9/L, and hemoglobin ≥90g/L (without transfusion or correction with G-CSF or other hematopoietic growth factors within 7 days);
- (9) Adequate liver function, defined as a total bilirubin level \leq 1.5 times the upper limit of normal (ULN) and levels of aspartate aminotransferase (AST) and alanine aminotransferase (ALT) \leq 2.5 times ULN for all patients;
- (10) Adequate renal function, defined as a creatinine clearance rate ≥50ml/min (Cockcroft-Gault formula);
- (11) Adequate coagulation function, defined as an international normalized ratio (INR) or prothrombin time (PT) ≤1.5 times ULN; if the subject is receiving anticoagulant therapy, as long as the INR/PT is within the range specified for the anticoagulant medication, it is acceptable;

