7.1.2 Tumor Imaging Assessment During the Study

Tumor imaging evaluations will be conducted every 6 weeks (±7 days) following the first dose of the study medication, and after 24 weeks of treatment, evaluations may be conducted every 9 weeks (±7 days) until disease progression, initiation of new anticancer treatment, subject withdrawal of ICF, or death. Patients who first record radiographic disease progression and meet specific conditions may continue treatment after disease progression.

If during the study, patients exhibit clinically unstable disease, unplanned imaging assessments can be conducted at any time.

The definition of clinically unstable disease is as follows:

- The appearance of clinically significant symptoms and signs indicating disease progression (including the deterioration of laboratory test values)
- A decrease in the ECOG PS score
- Rapid disease progression
- Tumor progression in important anatomical locations requiring other urgent medical interventions (such as spinal cord compression)

For patients who discontinue treatment for reasons other than radiographic disease progression, imaging assessments should be performed at the end of treatment, and then continue with imaging evaluations at the scheduled time points according to the protocol, until any of the following events occur: initiation of new anticancer treatment, objective

disease progression, subject withdrawal of ICF, loss to follow-up, or death.

If the investigator is unable to determine whether the disease has progressed, especially if there is uncertainty regarding non-target lesions and new lesions, subjects may continue treatment and undergo repeat imaging assessments when clinical symptoms occur or at the next scheduled assessment time. If disease progression is confirmed, the date of progression should be the initial date of discovery.

Tumor imaging assessments in this study are based on the investigator's use of RECIST 1.1, and the assessment method is detailed in Appendix 3.

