9.1 Sample Size Calculation

Based on previous study data, the 1-year PFS rate for patients with extensive-stage small cell lung cancer (SCLC) receiving first-line chemotherapy does not exceed 5.4%. We estimate that the use of first-line Sintilimab combined with chemotherapy can increase the 1-year PFS rate of patients to 15%. Through sample size calculation, with α =0.05 (one-sided test), Power=80%, and assuming a dropout rate of 10%, using the One-Sample Logrank Test, a total of 45 patients need to be enrolled.

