9.2 Statistical Analysis Plan

The statistical analysis endpoints for this study include:

Primary endpoint:

- To evaluate the 1-year PFS rate of subjects receiving first-line treatment with a PD-1 inhibitor combined with chemotherapy.

Secondary Endpoints:

- To evaluate the progression-free survival (PFS), overall survival (OS), and objective response rate (ORR) of subjects according to RECIST 1.1;
- To assess the quality of life of subjects based on the EORTC QLQ-C30 scoring;
- To evaluate the incidence of adverse events (AEs) in subjects.

Exploratory Endpoints:

- To identify potential predictive biomarkers of efficacy for immunotherapy in late-stage (extensive-stage) small cell lung cancer.

Statistical analysis will primarily utilize SPSS statistical software for programming and computation. Statistical tests will employ one-tailed and two-tailed tests; a P-value less than or equal to 0.05 will be considered to indicate a statistically significant difference, and confidence intervals will be reported at a 95% confidence level.

Patient Baseline Characteristics:

Calculate the mean, standard deviation, median, maximum, and minimum values for quantitative data such as age, height, and weight; list the frequency and percentage for qualitative data such as gender, ECOG score, etc.

Efficacy Analysis:

PFS and OS will be estimated using the Kaplan-Meier method to determine median values and their 95% CIs, and survival curves will be plotted. The objective response rate (ORR, which equals complete response [CR] plus partial response [PR]) and its 95% CI will be calculated. Quality of life scores will be compared with baseline values using paired t-tests or Wilcoxon signed-rank tests for within-group comparisons before and after treatment.

Safety Analysis:

Descriptive statistical analysis will primarily be used, with tables describing adverse events and adverse reactions (defined asadverse events 'definitely related/likely related/possibly

related' to the study drug) that occurred during the trial. Laboratory test results will describe conditions that were normal before the trial but abnormal after treatment, as well as the relationship between these changes and the study drug. Calculate the mean, standard deviation, median, minimum, and maximum values for vital signs and laboratory indicators before and after medication, using paired t-tests for before-and-after comparisons.

Compliance Analysis:

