2.7 Special Notes on Efficacy Assessment

When nodular lesions are included in the overall target lesion assessment and the size of these nodules decreases to a "normal" size (<10mm), they will still have a lesion size scan report. To avoid overestimating the situation reflected by the increase in nodule size, even if the nodule is normal, the measurement results will be recorded. As previously mentioned, this means that subjects with a complete response will not be recorded as 0 on the eCRF form.

If efficacy confirmation is required during the trial process, repeated "unevaluable" time points will complicate the best efficacy assessment. The trial's analysis plan must clarify how these missing data/assessments can be interpreted when determining efficacy. For example, in most trials, a subject's response of PR-NE-PR can be considered as having received efficacy confirmation.

When a subject experiences an overall deterioration in health that requires cessation of drug treatment, but without objective evidence, it should be reported as symptomatic progression. Even after treatment is discontinued, efforts should be made to assess the objective progression.

Symptomatic deterioration is not an assessment description of objective response; it is the reason for stopping treatment. The objective response of such subjects will be assessed through the target and non-target lesion conditions shown in Appendices 1 to 3.

Early progression, early death, and unevaluable situations are special cases of the study and should be clearly described in each protocol (depending on the treatment interval and treatment cycle).

In some cases, it is difficult to distinguish local lesions from normal tissue. When the assessment of complete response is based on such a definition, we recommend performing a biopsy before the efficacy assessment of complete response of local lesions. When some subjects' abnormal imaging results of local lesions are considered to represent lesion fibrosis or scar formation, FDG-PET is used as an assessment standard similar to biopsy for confirming complete response. In such cases, the application of FDG-PET should be

described prospectively in the protocol, and specifically for this situation.

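### The only written definition of the primary endpoint leaves out death, contradicts its own label of progression-free survival, and allows readings that raise the 1-year rate

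*Protocol*

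**What the plan says.** The Protocol Summary defines the endpoint: "The primary endpoint of this study is the 1-year PFS rate, defined as the proportion of patients without disease progression at one year". Progression is the only event in that sentence.

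Elsewhere the endpoint is named but not defined. The main objective in the synopsis is "To evaluate the 1-year Progression-Free Survival (PFS) rate of subjects receiving first-line treatment with PD-1 inhibitor combined with chemotherapy". Section 2.1 adds that the assessment is by the investigator under RECIST 1.1. Section 9.2 repeats the label: "To evaluate the 1-year PFS rate of subjects receiving first-line treatment with a PD-1 inhibitor combined with chemotherapy". For the analysis it says "PFS and OS will be estimated using the Kaplan-Meier method to determine median values and their 95% CIs, and survival curves will be plotted", without stating what counts as an event.

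On tumour assessment, death appears in 7.1.2 as a reason to stop imaging, which runs "until disease progression, initiation of new anticancer treatment, subject withdrawal of ICF, or death". Outside the endpoint, death appears as a reason to end treatment, as a safety outcome and through OS.

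The sample size sections (3.1.1 and 9.1) set the benchmark, saying that the rate for patients "receiving first-line chemotherapy does not exceed 5.4" per cent, and the target, that the combination "can increase the 1-year PFS rate of patients to 15" per cent. They name a one-sample log-rank test, one-sided α of 0.05, 80% power, 10% dropout and 45 patients.

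**The concern.** A rate of progression-free survival at one year normally requires the patient to be alive. The written definition drops that requirement. Someone who dies at month four with no progression on a scan has had no event under the definition, and because imaging stops at death, none can be recorded later.

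Two scorings are then open. In a simple proportion, the patient may be counted among those without progression. In a Kaplan-Meier or log-rank analysis, the patient may be censored at death. Both push the estimate up.

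Such deaths are plausible in this population. Patients with ECOG 2 and an expected survival of only three months are eligible, and scans are six weeks apart, then up to nine. The trial is single-arm, open-label and investigator-assessed, with a gap of 9.6 percentage points between benchmark and target. How deaths are scored should therefore not remain open once data have been seen.

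**Working it through.** **Comparison of the sections.** The synopsis definition names progression only. The synopsis objectives and evaluation criteria, 2.1, 2.2, 9.1, 9.2 and the RECIST excerpt use the term PFS or give response rules. None states that death from any cause is a PFS event, so nothing corrects the synopsis sentence.

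**Reproducing the plan's own figure.** Inputs from 9.1 are 5.4%, 15%, one-sided α 0.05, power 80% and dropout 10%. I assume exponential PFS.
- Hazards per year: −ln(0.054) = 2.919 and −ln(0.15) = 1.897. Hazard ratio = 1.897/2.919 = 0.650.
- n = [z(0.95)·√E0 + z(0.80)·s1]² / (E0 − O1)². E0 and O1 are the expected null cumulative hazard and the expected events per patient under the alternative. s1 is the standard deviation of their difference under the alternative.
- Accrual and follow-up are not stated, so I assume them. Accrual of 0.5 or 1 year with 1 year minimum follow-up gives n = 39.7 or 39.1, that is 40 evaluable. Then 40/0.9 = 44.4, rounded up to 45.
- Over 0–2 years of accrual and 1–2 years of follow-up the total runs from 44 to 47.

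The stated 45 is reproduced, and it rests on the log-rank test. An exact single-stage binomial test would need 59 evaluable patients.

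**Size under the stated methods (deaths censored).** Let d be the share of all patients who die in year one without documented progression. The protocol gives no value, so d = 3%, 5% and 10% are assumptions. With constant hazards and a true 1-year PFS rate of 5.4%, 94.6% of patients have an event in year one, and a fraction d/0.946 of those events are such deaths. Censoring them leaves only the progression hazard:

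apparent rate = 0.054^(1 − d/0.946)

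- d = 3%: 0.054^0.968 = 5.9%
- d = 5%: 0.054^0.947 = 6.3%
- d = 10%: 0.054^0.894 = 7.4%

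I simulated the one-sample log-rank test, Z = (O − E)/√E, with 45 patients, one-sided 0.05, accrual of 0 to 1 year and 1 year minimum follow-up.

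| d | Rejection probability at a true rate of 5.4% |
|---|---|
| 0 | about 4% |
| 3% | about 6% |
| 5% | about 8% |
| 10% | about 15% |

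**Size under the literal proportion (deaths counted as successes).** Apparent rate = 5.4% + d, which gives 8.4%, 10.4% and 15.4%. Each such death adds 1/45 = 2.2 percentage points. The whole assumed gain is 15 − 5.4 = 9.6 points, or 0.096 × 45 = 4.3 patients.

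**The case against.** The strongest reply is that the endpoint is called progression-free survival, and a dead patient is not surviving progression-free. The sponsor may well intend death to count. That stands as far as it goes: a reader might infer that deaths will be scored as successes, and the document does not support that certainty. The wording permits the scoring but does not establish it. What remains is that the explicit definition and its label disagree, and no other section says which governs.

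A second reply concerns size. A reader might conclude that 10% of such deaths would produce the whole target effect, since 15.4% exceeds 15%. One might go further and set a rule such as 6 successes in 45, under which false-positive probability would rise from 3.3% to 71%. The protocol states no such proportion test or cutoff. It names a one-sample log-rank test and Kaplan-Meier estimation, under which an uncounted death would normally be censored, with the smaller effects shown above. The word proportion in the definition is the only support for the cruder count.

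Three further limits also stand.
- Section 7.1.2 allows unplanned imaging for clinically unstable disease, so some deaths from clinical progression would have a progression record first.
- Appendix 3 says "Early progression, early death, and unevaluable situations are special cases of the study and should be clearly described in each protocol". This is general RECIST guidance on classifying response, so it adds little on the PFS event.
- The source of the 5.4% is not shown. That it counts deaths follows from the usual meaning of PFS and cannot be verified here.

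The point is not answered by leaving the matter to a statistical analysis plan. The protocol has fixed a definition, and a plan that counted death as an event would depart from it.

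**Conclusion.** The point holds as a misstated definition of the primary endpoint: it omits death and contradicts its own label. The bias under either literal reading runs in one direction, upward. Under the stated methods with deaths censored it is moderate: for an assumed 3% to 10% of deaths without documented progression, the apparent rate moves from 5.4% to between 5.9% and 7.4%, and false-positive probability from about 4% to between 6% and 15%. Under a crude proportion the apparent rate would be 8.4% to 15.4%. That two readings of one sentence give 7.4% and 15.4% at the same 10% is the reason to settle it before analysis.

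These figures assume constant hazards, the chosen death shares, accrual of up to one year and one year of minimum follow-up. The contradiction in the text depends on none of them.

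**What to change.** Define the PFS event as RECIST 1.1 progression or death from any cause, whichever comes first. Define the 1-year PFS rate as the proportion of patients alive and free of RECIST 1.1 progression at one year. Use identical wording in the synopsis, 2.1 and 9.2.

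The cost is one sentence in three places. The sample size stays at 45, provided that the 5.4% and 15% are PFS rates in the usual sense. The only downside is an estimate that may be slightly less favourable.

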influenza are permitted; however, live attenuated influenza vaccines administered nasally are not allowed; (19) Have a medical history, disease, treatment, or laboratory abnormalities that may interfere with the trial results, prevent full participation in the study, or that the investigator deems participation in the study is not in the best interest of the subject; (20) Have local or systemic diseases caused by non-malignant tumors, or secondary reactions to cancer that could lead to increased medical risks and/or uncertainty in the evaluation of life expectancy. (21) The investigator deems the subject unsuitable for inclusion. 1. Sintilimab: 100 mg/10 ml, 200 mg, administered via intravenous infusion on Day 1, Q3W (every 3 weeks) 2. Carboplatin: AUC 5 mg/ml/min, administered via intravenous infusion on Day 1, Q3W Study 3. Cisplatin: 20 mg/vial, 75 mg/m^2, administered via intravenous Medication infusion on Day 1, Q3W and Administration 4. Etoposide: 100 mg/5 ml, 100 mg/m², administered via intravenous Method infusion on Days 1-3, Q3W Continue until disease progression, death, intolerable toxicity, withdrawal of informed consent, initiation of new antitumor treatment, or termination for other reasons specified in the protocol, with a maximum duration of Sintilimab use of 2 years. Therapeutic Efficacy Assessment: - The investigator will assess therapeutic efficacy according to RECIST 1.1. The evaluation includes progression-free survival (PFS), 1-year PFS rate, overall survival (OS), and objective response rate (ORR). Safety Assessment: **Evaluation** - The incidence, relationship to the study medication, and severity of Criteria all adverse events (AEs), treatment-related adverse events (TRAEs), immune-related adverse events (irAEs), and serious adverse events (SAEs); - The number of subjects who discontinue the study due to the aforementioned adverse events: - Changes in vital signs, physical examination results, and laboratory results before, during, and after the study treatment.

The statistical analysis primarily employs programming calculations using the SPSS statistical analysis software. Statistical tests utilize one-tailed and two-tailed tests, with a P-value less than or equal to 0.05 considered to indicate a statistically significant difference, and the confidence interval adopts a 95% confidence level.

Statistical Methods

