4.4 Criteria for Subject Discontinuation of Treatment/Withdrawal from the Study

4.4.1 Discontinuation of Study Treatment

Discontinuation of study treatment does not mean withdrawal from the study. Since certain clinical event data after discontinuation of treatment may be very important for the study, this information must be collected up to the subject's last scheduled visit, even if the subject has already stopped treatment.

Subjects may discontinue treatment at any time for any reason, or the researcher may decide whether to discontinue their treatment when any adverse event occurs. In addition, if the subject is not suitable for treatment, violates the study protocol, or for management and/or other safety reasons, the researcher or sponsor may discontinue the subject's treatment.

For any of the following reasons, the subject must discontinue treatment but can continue to be monitored in the study:

- The subject or the subject's legal representative requests to discontinue treatment.
- An adverse event occurs that requires treatment to be stopped as stipulated in the protocol (refer to Section 5.2).
- Another malignant tumor requiring active treatment occurs.
- A concurrent disease occurs that prevents further treatment.
- The researcher decides to withdraw the subject from the study.
- The subject's serum pregnancy test result is positive.
- The subject has poor compliance.
- The researcher and/or the sponsor believes that continuing to administer the study drug will place the subject at unnecessary risk based on the subject's disease condition or personal situation.
- Completion of 2 years of sintilimab treatment.

For subjects who have discontinued treatment but continue to be visited in the study, all visits and procedures listed in the study flowchart should be completed.

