4.4.2 Withdrawal from the Study

If the subject or the subject's legal representative withdraws the informed consent to participate in the study, the subject must withdraw from the study. If the subject withdraws from the study, they will no longer receive treatment or scheduled visits. With the subject's consent, the subject can receive survival follow-up after withdrawing from the study. If the subject is lost to follow-up, they must withdraw from the study.

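### The Summary's safety criterion counts subjects who leave the study because of adverse events, although the protocol keeps toxicity stops in follow-up, so as written it undercounts toxicity-related discontinuation

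*Protocol*

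**What the plan says.** In the Protocol Summary, the safety part of the Evaluation Criteria row has three items: AE incidence, relationship and severity; a discontinuation count; and changes in vital signs, examinations and laboratory results. The second item reads "The number of subjects who discontinue the study due to the aforementioned adverse events". The events meant are those of the item before it: AEs, treatment-related AEs (TRAEs), immune-related AEs (irAEs) and serious AEs (SAEs).

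Section 4.4 treats stopping treatment and leaving the study as different events.

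- Section 4.4.1 opens with "Discontinuation of study treatment does not mean withdrawal from the study". It then lists reasons for which "the subject must discontinue treatment but can continue to be monitored in the study". One of them is "An adverse event occurs that requires treatment to be stopped as stipulated in the protocol". Another is "The researcher decides to withdraw the subject from the study".
- Section 4.4.2 covers leaving the study. Where a subject or legal representative "withdraws the informed consent to participate in the study, the subject must withdraw from the study". Loss to follow-up is the other case it names. An AE is not named there.

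Two further sections say where toxicity stops go. Section 3.1 moves a patient whose treatment ends for intolerable toxicity to the post-treatment visit and then to survival follow-up. Section 5.2.1 has a subject who cannot resume sintilimab within 12 weeks stop it permanently and enter the follow-up phase, with two stated exceptions.

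**The concern.** A discontinuation count in a safety list is there to show how many patients could not stay on treatment because of toxicity. The item as worded counts a different event, departure from the study. The protocol deliberately keeps patients in the study after a toxicity stop, so the better the site follows Sections 3.1, 4.4.1 and 5.2.1, the lower the literal count, whatever the true frequency of toxicity stops.

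This affects a figure that will be read as a tolerability result for a combination with a safety lead-in. It also leaves room for two analysts to report different numbers from the same data, one counting treatment stops and the other counting study exits, with the choice made after the data are seen.

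**Working it through.** The protocol gives no expected number of AE-related discontinuations, so there is no figure to reproduce. The check is a comparison of sections, followed by an illustration of size.

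**Comparison of sections**

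1. Event counted by the criterion: leaving the study because of an AE (Summary, Evaluation Criteria).
2. Status of a protocol-required AE stop: a treatment discontinuation, after which monitoring can continue (4.4.1).
3. Destination of such a patient: post-treatment visit and survival follow-up (3.1), or the follow-up phase (5.2.1). Imaging continues after a stop for reasons other than progression (7.1.2, 7.1.3).
4. Events named as leaving the study: consent withdrawal and loss to follow-up (4.4.2), investigator decision (an item in the 4.4.1 list), and pregnancy of a female subject (8.5).
5. Hence a patient who permanently stops sintilimab under Table 4, for example for Grade 4 diarrhea or enterocolitis, and stays in follow-up adds nothing to the literal count.

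**Illustration of size**

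Inputs:
- N = 45, planned enrolment (Summary and Section 3.1).
- t = share of patients who stop study drug for an AE. Assumed at 5%, 10% and 20%.
- w = share of those patients who also leave the study for it. Assumed at 0%, 10% and 30%, with 100% as the limit at which the two counts agree.

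Formulas:
- Expected drug stops = N × t
- Expected literal count = N × t × w
- Probability that the literal count is zero = (1 − t × w)^N

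| t | Drug stops, 45 × t | w | Literal count, 45 × t × w | P(count = 0) |
|---|---|---|---|---|
| 5% | 2.25 | 0% | 0 | 1.000 |
| 5% | 2.25 | 10% | 0.225 | 0.798 |
| 5% | 2.25 | 30% | 0.675 | 0.507 |
| 5% | 2.25 | 100% | 2.25 | 0.099 |
| 10% | 4.5 | 0% | 0 | 1.000 |
| 10% | 4.5 | 10% | 0.45 | 0.636 |
| 10% | 4.5 | 30% | 1.35 | 0.254 |
| 10% | 4.5 | 100% | 4.5 | 0.009 |
| 20% | 9 | 0% | 0 | 1.000 |
| 20% | 9 | 10% | 0.9 | 0.403 |
| 20% | 9 | 30% | 2.7 | 0.062 |
| 20% | 9 | 100% | 9 | 0.000 |

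The expected shortfall is N × t × (1 − w). For w between 0% and 30% it runs from 45 × 0.05 × 0.7 = 1.575 patients (3.5 percentage points) to 45 × 0.20 × 1 = 9 patients (20 percentage points). It is positive whenever w is below 100%.

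**The case against.** The strongest reply is that the protocol does not hold to its own distinction, so the literal reading is not the only one. Section 6.3.1 runs treatment discontinuation and study withdrawal together as one event. A positive pregnancy test is a treatment stop with possible monitoring in 4.4.1 but a study withdrawal in 8.5. The headings within 4.4 pair discontinuation with treatment and withdrawal with the study, and the criterion uses the former verb. An investigator could therefore read it as discontinuing study treatment. This stands as a description of loose usage. It does not rescue the wording, because it confirms that the count can be run in two ways.

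A reader might infer that an AE can never take a patient off study, and that the count will be about zero whatever the toxicity. The documents do not support this. Section 4.4.1 permits continued monitoring but does not guarantee it, and it lists withdrawal by the investigator. Toxicity may also prompt consent withdrawal. Section 4.4.2 says when a subject must leave, not that there is no other route.

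A reader might also infer that toxicity would be hidden. That goes too far. The preceding Summary item reports the incidence, relationship and severity of all AEs, so a severe irAE would still appear. Section 7.2 has each AE characterized by, among other things, the action taken on treatment, and the Compliance Analysis in Section 9.2 summarises completion of treatment cycles, though not by reason for stopping.

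Finally, the absence of such a count from the safety analysis in 9.2, and of full tables for every drug, is not a defect on this evidence. A statistical analysis plan, not shown here, may hold that detail.

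**Conclusion.** The criterion is wrong as written. It names study discontinuation where the protocol's own rules make an AE stop a treatment discontinuation followed by continued follow-up. Applied literally, it undercounts AE-related stops by every patient who stops drug for an AE and does not also leave the study.

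The direction of the error follows from the text, but its size does not. The illustrated shortfall of about 1.6 to 9 patients of 45 rests entirely on the assumed stop rates of 5% to 20% and the assumed share leaving the study of 0% to 30%. A zero count is certain only if no such patient leaves; its probability falls to about 6% at the other end of that range (t = 20%, w = 30%).

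The item is an evaluation criterion in the Summary. The safety endpoint named in Section 9.2 is AE incidence. No hypothesis, decision rule, sample size or primary analysis depends on the item. The correction is still worth making, because it changes a safety figure that would be reported and costs almost nothing.

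**What to change.** Reword the Summary criterion as: number and proportion of subjects who permanently discontinue study treatment (any study drug, and sintilimab separately) due to an AE, TRAE, irAE or SAE. Report withdrawal from the study, with its reason, as a separate disposition count.

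The cost is one line of wording and one tabulation. Section 7.2 already has the action taken on treatment recorded for AEs, so no new data collection is needed, and no treatment or follow-up rule changes. The only drawback is that the reported safety figure may look less favourable than the literal count.
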